8.6 Missing Date Handling

• Adverse Event with missing or partial missing date :

Adverse Event with incomplete start date will be considered as treatment emergent if:

- a. Day and month are missing and the year is equal to or after the year of the first dosing date;
- b. Day is missing, and the year is after the year of the first dose;
- c. Day is missing and the year is equal to the year of the first dosing date and the month is equal to or after the month of the first dosing date;
- d. Year is missing; or
- e. Complete date is missing.
- Therapy (medication, procedure, radiotherapy) date missing or partial missing: See Section 5.2.5 for the missing date handling in determination of prior and concomitant medications. For the case of missing efficacy data, see Section 5.4. For other cases, detail of handling will be provided in a separate document (analysis datasets specification).

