5.6.2 Adverse Events

The AE verbatim descriptions (investigator terms from the CRF) will be classified into standardized medical terminology using the Medical Dictionary for Regulatory Activities (MedDRA). Adverse events will be coded to the MedDRA (Version 19.1 or higher) lower level term (LLT) closest to the verbatim term. The linked MedDRA preferred term (PT) and primary system organ class (SOC) will also be captured in the database. The CTCAE grading (Version 4.03 or higher) will be considered in the database.

A treatment-emergent adverse event (TEAE) is defined as an AE that emerged during treatment (i.e., AE onset or worsening is on or after first dose date of any study drugs, or up to 28 days following last dose of any study drugs), having been absent at pretreatment (Baseline) or

- Reemerged during treatment, having been present at pretreatment (Baseline) but stopped before treatment, or
- Worsened in severity during treatment relative to the pretreatment state, when the AE was continuous.

Only those AEs that are treatment emergent will be summarized in tables. A subject will be counted only once within each category (ie, SOC, PT, grade, or other specific category to be summarized in table) even if the subject experienced more than 1 TEAE within the category. All AEs, treatment emergent or otherwise, will be presented in subject data listings.

The following TEAE summary analyses will be performed:

• An overview summary table will include number (percentage) of subjects with any TEAE, with any treatment-related TEAE, with any TEAE of grade 3 or above, with any TEAE of grade 3 or grade 4, with any serious TEAE, with any TEAE leading to study drug withdrawal, with any TEAE leading to study drug dose reduction, with any TEAE

leading to study drug interruption, and with any TEAE of special interest. This overall summary will be repeated similarly for treatment-related TEAEs.

- TEAEs will be summarized by SOC, PT and grade in number (percentage) of subjects. Repeat this analysis for the TEAEs that are treatment-related, serious, serious and treatment-related, leading to death/dose modification/dose discontinuation, separately.
- TEAEs will be summarized by PT and grade in number (percentage) of subjects.
- Fatal TEAEs will be summarized by SOC and PT in number (percentage) of subjects. Repeat this analysis for non-fatal TEAEs, for TEAEs leading to study dose withdrawn, and for TEAEs leading to study dose reduction/interruption, separately.

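### SAP 8.6 counts some adverse events with incomplete start dates as treatment-emergent even when the record places them outside the SAP 5.6.2 window

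*SAP*

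**What the plan says.** SAP 5.6.2 (Adverse Events) defines a TEAE as an event that emerged during treatment, and explains the timing as: "AE onset or worsening is on or after first dose date of any study drugs, or up to 28 days following last dose". It adds a condition relative to baseline. The event must qualify through "having been absent at pretreatment (Baseline) or" one of two alternatives: re-emergence after having stopped before treatment, or worsening of a continuing event. Only TEAEs are tabulated. All AEs are listed.

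SAP 8.6 (Missing Date Handling) has a separate rule for incomplete dates. It opens: "Adverse Event with incomplete start date will be considered as treatment emergent if" any of five conditions holds.

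- **Rule a:** "Day and month are missing and the year is equal to or after the year of the first dosing date".
- **Rule b:** "Day is missing, and the year is after the year of the first dose".
- **Rule c:** day missing, year the same as the first dose, month the same or later.
- **Rules d and e:** the year, or the whole date, is missing.

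Two neighbouring sections use the same boundary. SAP 5.2.5 calls a medication prior if it stopped before the first dose, and ends the concomitant period 28 days after the last dose. It defaults to concomitant only when the dates leave the class undetermined. SAP 5.6.2.1 splits deaths at 28 days after the last dose.

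**The concern.** Section 8.6 does not impute a date for 5.6.2 to test. It assigns the status outright, and each rule that uses a date compares it with the first dose alone. Treating an event of unknown timing as treatment-emergent is an ordinary cautious default. These rules go further, because they also capture events whose timing is known well enough to rule them out.

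What is at stake is the content of the TEAE tables. SAP 8.1 reports everything by dose level and the groups are small, so a single event in the wrong class can be visible in a row. The error can only add events to the tables.

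**Working it through.** The plan states no figure on this point, so there is nothing to reproduce. The check applies the written rules to test records.

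**Inputs.** The window comes from SAP 5.6.2 and rules a to e from SAP 8.6. The dose dates are assumed for illustration, since the documents give none: first dose 15 Mar 2017, last dose 1 Aug 2017. The window then ends on 1 Aug + 28 days = 29 Aug 2017.

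**Step 1: incomplete start dates.** The repaired rule excludes an event if its stop date is before the first dose, or if its earliest possible onset is after the window ends.

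| Start | Stop | Rule met in 8.6 | 8.6 result | What the record shows | Repaired rule |
|---|---|---|---|---|---|
| 2017 | 20 Feb 2017 | a | TEAE | ended before first dose | not TEAE |
| wholly missing | 20 Feb 2017 | e | TEAE | ended before first dose | not TEAE |
| Mar 2017 | 10 Mar 2017 | c | TEAE | ended before first dose | not TEAE |
| Oct 2017 | none | c | TEAE | earliest onset 1 Oct 2017 | not TEAE |
| 2018 | none | a | TEAE | earliest onset 1 Jan 2018 | not TEAE |
| Feb 2018 | none | b | TEAE | earliest onset 1 Feb 2018 | not TEAE |
| Mar 2017 | none | c | TEAE | undetermined | TEAE |
| May 2017 | none | c | TEAE | inside the window | TEAE |
| 2016 | none | no rule | not TEAE | before first dose | not TEAE |

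The first six records are misclassified by 8.6, and the repair corrects all six. The last three are unchanged.

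**Step 2: which rules are affected.** A stop date before the first dose can occur under rules a, c, d and e. It cannot occur sensibly under rule b, where the start year is already later than the first-dose year. Onset known to be too late can occur under rules a, b and c. Under d and e no year is known, so lateness cannot be shown.

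**Step 3: complete dates.** I applied the 5.6.2 date test to 1,095 consecutive days, starting 365 days before the assumed first dose.

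- With *or*, all 1,095 days pass, because any date is either on or after the first dose or no later than 29 Aug 2017.
- With *and*, 168 days pass: 17 + 30 + 31 + 30 + 31 + 29, from 15 March to 29 August inclusive.

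A test that also admits every pre-dose date contradicts the sentence it explains, so *or* cannot be what was meant.

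**Step 4: possible size in a table.** SAP 3.2.1 plans 6 subjects per run-in cohort and 18 in total at the recommended dose. One subject wrongly counted in a row adds at most 1/6 = 16.7 percentage points or 1/18 = 5.6 points. SAP 5.6.2 counts a subject once per category, so the shift is zero if that subject has another TEAE in the row.

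**The case against.** The strongest reply is that 8.6 is conservative by design and sits beside a definition that does state an end of window. Much of this stands. Counting an event whose date is unknown is defensible, and the repair keeps that default. But caution about unknown timing does not extend to events that the record shows to be outside the window. SAP 5.2.5 makes this distinction for medications.

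A reader might infer from the *or* that the TEAE rules have no working end of window at all, or that any AE resolved before the first dose would be counted. The documents do not support either. Section 5.6.2 names the 28-day limit, and 5.2.5 and 5.6.2.1 use the same limit. A fully dated event that ended before the first dose did not emerge, re-emerge or worsen on treatment, so 5.6.2 excludes it.

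A second reply is that SAP 9 leaves derivation rules to a separate analysis datasets specification, which might contain the missing checks. That document is not available, so this cannot be ruled out. A specification that did so would, however, depart from an explicit SAP rule. The deferral of other cases within 8.6 itself belongs to the bullet on therapy dates, not the one on AEs.

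A third reply is that the problem may seldom arise. Medical history is recorded separately (SAP 5.2.4). The End of Treatment visit falls within 30 days of the last dose, and the follow-up described in SAP 3.2.3 covers disease status and survival. The supplied text gives no AE collection period. This stands: the frequency is unknown and may be low.

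**Conclusion.** Wrong as written, minor. For AEs with incomplete start dates, SAP 8.6 gives a result contrary to 5.6.2 in two situations: the stop date precedes the first dose, or the known part of the start date is already more than 28 days after the last dose. The conjunction in 5.6.2 also needs correcting, but the intended meaning is clear.

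The total effect cannot be computed, because the documents give no count of incomplete dates. The 16.7- and 5.6-point figures are ceilings for one subject in one row. They assume the planned group sizes, since the numbers actually treated are not given.

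A reader might also infer that the recommended Phase 2 dose is at risk. The documents do not support that. The dose decision rests on dose-limiting toxicities in the first cycle (SAP 3.2.1 and 5.6.6.1), and nothing ties those to the TEAE flag. Nor do the documents show that pre-study symptoms or events after later therapy enter the AE data. The consequence is limited to possible over-counting in the TEAE tables. The listings are unaffected.

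**What to change.** Make two edits.

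1. **SAP 5.6.2:** change the *or* before the 28-day bound to *and*, so that onset or worsening must satisfy both limits.
2. **SAP 8.6:** put this exception in front of rules a to e: *unless the latest date compatible with the known parts of the stop date is before the first dose date, or the earliest date compatible with the known parts of the start date is more than 28 days after the last dose of any study drug*. State that events which remain undetermined stay treatment-emergent.

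The exception settles partial stop dates. With the assumed first dose of 15 Mar 2017, a stop date of Feb 2017 excludes the event, because its latest possible day is 28 Feb. A stop date of Mar 2017 does not, because its latest possible day is 31 Mar. A wholly missing stop date excludes nothing.

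The cost is two sentences in the SAP and a small change to the derivation code. The SAP introduction says the plan is to be final before database lock, which is when the edits belong. No new data are needed.

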8.7 Unscheduled Visit

Data from unscheduled visits (eg, vital signs or laboratory tests) will be excluded from the by-visit summary but will contribute to the worst value in required summary tables. Listings will include all, the scheduled and unscheduled.

9 PROGRAMMING SPECIFICATIONS

The rules for programming derivations and dataset specifications will be provided in separate document (analysis datasets specification).

10 STATISTICAL SOFTWARE

All statistical analyses will be performed using SAS version 9 or higher.

11 MOCK TABLES, LISTINGS, AND GRAPHS

The study TLG shells will be provided in a separate document, which will show the content and format of all tables, listings, and graphs in detail.

